7.2 Termination of the Study

The Sponsor reserves the right to discontinue this study at any time. The Investigator, in collaboration with the Sponsor, reserves the right to discontinue the study for safety reasons at any time.

7.3 Monitoring

The responsible study monitor(s) will contact and visit the study sites as necessary, and he/she will be allowed, upon request, to inspect and verify all records of the study (e.g.,

source document, ICFs, CRFs, regulatory documents) in a manner consistent with GCP and all other applicable state and federal law.

It will be the study monitor's responsibility to inspect the source documents to verify the adherence to the protocol and the completeness, consistency, and accuracy of the data being entered in the CRF. The monitor will verify that each subject has consented in writing prior to any study procedures being performed. Where the terms of the Informed Consent, GCP, and all other applicable state and federal law permit, the monitor should have access to laboratory test reports and other subject records needed to verify the entries on the CRF. The Investigator (or his/her designee) agrees to cooperate with the monitor to ensure that any issues detected in the course of these monitoring visits are resolved.

In addition, the Sponsor's internal auditors (or designee) and government inspectors may evaluate the study and must be allowed access to CRFs, source documents, and other study files.

The Investigator must notify the Sponsor (or designee) promptly of any inspections of the study or activities related to the study scheduled by regulatory authorities, allow the Sponsor (or designee) to be present, and promptly forward copies of inspection reports to the Sponsor (or designee).

7.4 Data Quality Assurance

SOPs are available for all activities performed at Celerion relevant to the quality of this study. Designated personnel of Celerion will be responsible for maintaining quality assurance (QA) and quality control to ensure that the trial is conducted, and that data are generated, documented and reported in compliance with the study protocol, GCP, and GLP requirements as well as applicable regulatory requirements. All activities performed will be reported in the QA certificate and will be included in the study report.

All clinical data will undergo a 100% quality control check prior to clinical database lock. Edit checks are then performed for appropriate databases as a validation routine using SAS to check for missing data, data inconsistencies, data ranges etc. Corrections are made prior to database lock.

7.5 Direct Access to Source Data/Documents

The Investigator will prepare and maintain adequate and accurate source documents and agree that the Sponsor, its representatives, the IRB, and representatives from worldwide regulatory agencies will have the right to review and inspect pertinent records related to the clinical trial both during and after the clinical trial. Examples of source documents may include the study product inventory, study product label records, CRFs, recorded data from automated instruments, and other primary records that are relevant to this clinical trial. These documents are designed to record all observations and other pertinent data for each subject enrolled in this clinical trial.

7.6 Data Handling and Record Keeping

Each CRF will be reviewed and signed off by the Investigator within the electronic data capture system.

All raw data generated in connection with this study, together with the original copy of the final report, will be retained by the sites until at least 5 years after the last approval of a

marketing application in an ICH region and until there are no pending or contemplated marketing applications in an ICH region or at least 5 years have elapsed since the formal discontinuation of clinical development of the investigational product. These documents should be retained for a longer period, however, if required by the applicable regulatory requirements or by an agreement with the Sponsor. It is the responsibility of the Sponsor to inform the Investigator/Institution as to when these documents no longer need to be retained.

7.7 Publication Policy

All unpublished information given to Celerion by the Sponsor shall not be published or disclosed to a third party without the prior written consent of the Sponsor.

The data generated by this study are considered confidential information and the property of the Sponsor. This confidential information may be published only in collaboration with participating personnel from the Sponsor or upon the Sponsor's written consent to publish the information.

8. DATA MANAGEMENT

Data management activities will be detailed in the Data Management Plan (DMP). Each vendor involved with this study will adhere to Good Documentation Practices and their standard operating procedures covering their respective activities relevant to participation in this study. The Investigator will ensure that all data related to the conduct of this study at his/her site is attributable, legible, contemporaneous, original, accurate, enduring, and readily accessible.

8.1 Database Design and Creation

An appropriate database will be designed and created within a validated Clinical Data Management System (CDMS). Electronic data capture will be used for this study and electronic case report form (eCRFs) will be developed according to the study protocol specifications. Clinical and analytical laboratory data will be collected external to CDMS as external data files.

8.2 Data Coding

AEs and medical history coding will be undertaken using most current version of MedDRA®. Concomitant medications coding will be undertaken using the WHO Drug Dictionary. Each dictionary version will remain the same throughout the trial. Coding will be completed by qualified members of the Celerion staff.

8.3 Data Entry and Verification

Data will be transcribed from original sources by the Investigator or Investigator's staff into the eCRF. External data received from clinical and analytical laboratories (clinical laboratory results) will be integrated into the Clinical Data Interchange Standards Consortium study data tabulation model datasets.

8.4 Study Results Data Transfer

Study data transfers will be sent to the Sponsor or their designee, electronically on a schedule and in a format mutually agreed upon by the Sponsor or their designee, and Celerion for the analysis of these study data. No personally identifiable information will be transferred to the Sponsor at any point in the study.

8.5 Data Validation

After the data have been entered and source data verified by the monitor, various edit checks (including manual review of listings) will be performed to ensure the accuracy, integrity and validation of the database against the eCRF as described in the DMP.

Inconsistencies that arise from these edit checks will be resolved with the Investigator or designee.

8.6 Database Lock

On study completion, after data entry is complete, the data has been pronounced clean, and the Investigators have reviewed and provided approval via signature, the database will be locked and final write access will be removed.

The Sponsor will be required to provide database lock approval.

Any changes to the data following database lock will be documented and approved by the Sponsor prior to unlocking the database to make changes to the data.

The final transfer of all study data (without subject personally identifying information) to the Sponsor will be in SAS format with supporting SAS documentation according to the specifications of the Sponsor. Subject initials, serology results, date of birth (except year), and other personal identifiers will be removed from this data transfer file; any such information removed will be documented at the time of transfer.

9. REPORTING

9.1 Case Report Forms

CRFs will be used for each screened subject whether or not he/she has completed the study. The Investigator will assure complete and accurate entries on the forms. All CRFs will be reviewed and signed by the Investigator.

9.2 Study Report

According to the ICH Harmonized Tripartite Guideline (Organization of the Common Technical Document for the Registration of Pharmaceuticals for Human Use M4 and the ICH M2 Expert Working Group), the final report will be written according to the ICH E3 Guideline (Structure and Content of Clinical Study Reports).

The report will be provided by Celerion to the Sponsor. The report will include a description of the clinical conduct of the study, safety evaluation, analytical methods and results, and the statistical analysis described in the statistical methodology section of the protocol and the SAP.

At the time the draft study report is completed, Celerion's QA unit will audit the report against the SAS data and the raw data. At the completion of the audit, a QA report will be issued internally allowing any findings to be addressed before report finalization.

10. GENERAL

10.1 Confidentiality

All members of the Investigator's staff and vendors will have signed confidentiality agreements with Celerion. Celerion will regard all information provided to the Investigators dealing with the study and information obtained during the course of the study as confidential.

The CRUs will not supply to the Sponsor any subject names, initials, date of birth (except year), or other personal identifiers.⁷ All such information appearing on any study document must be redacted before a copy of the document is supplied to the Sponsor. Study findings stored on a computer will be stored in accordance with local data protection laws. The subjects will be informed during the consenting process that representatives of the Sponsor, IRB, or regulatory authorities may inspect their medical records to verify the information collected, and that all personal information made available for inspection will be handled in the strictest confidence and in accordance with local data protection laws.

10.2 Responsibility of the Investigator

The Investigator is responsible for ensuring that the clinical study is performed in accordance with GCP based on the current ICH Guideline for GCP, the corresponding sections of the US CFR governing Protection of Human Subjects (Title 21 CFR Part 50), Institutional Review Boards (Title 21 CFR Part 56), the Basic Principles of the Declaration of Helsinki, and other applicable legal and regulatory requirements.

The Investigator should ensure that all persons assisting with the study are qualified for the duties assigned, adequately informed and trained on the protocol and amendments to the protocol, the study products, and their study-related duties and functions.

The Investigator will maintain a list, including signatures, of sub-investigators and other appropriately qualified persons to whom significant study-related duties are delegated. Any personnel change in this list during the course of the study will be documented. All study related training will be documented.

10.3 Procedure for Amendments to Protocol

No deviations from this protocol will be permitted, except in a medical emergency. The Investigator and the Sponsor will discuss any amendment to this study. If agreement is reached concerning the need for modification, this agreement will be made in a formal amendment to the protocol.

All revisions and/or amendments to the protocol must be approved, if applicable, in writing by Chesapeake IRB.

All persons who are affected by the amendment to the protocol will be retrained if deemed necessary.

10.4 Institutional Review Board

This protocol and ICFs will be reviewed and approved in writing by the IRB prior to commencement of the study. The study will not be initiated without the approval from the IRB. Any amendments after protocol approval, if applicable, will be reviewed and approved by the IRB prior to implementation. The IRB operations are in compliance with Title 21 CFR Part 56. Notice that the IRB approved protocol, ICF and any amendments to the protocol and ICF will be in the final study report.

10.5 Study Record Retention

Investigator-specific essential documents and all primary data and copies thereof (e.g., CRFs, laboratory records, data sheets, correspondence, photographs, computer records,), which are a result of the original observations and activities of the study and are necessary for the reconstruction and evaluation of any study report will be retained in the investigative site's archives for a minimum of 20 years after the completion or termination of the study. It is the responsibility of the Sponsor to inform the Investigator as to when these documents no longer need to be retained. The study report and final database will be retained in Celerion's archives for a minimum of 20 years after the completion or termination of the study and will be available for inspection at any time by the Sponsor. At completion of the study (i.e., at issuance of final study report), the final database will be transferred to the Sponsor. Subject initials, serology results, date of birth (except year), and other personal identifiers) will be redacted from this data transfer file; any such information removed will be documented at the time of transfer.

APPENDIX 1. Fagerström Test For Cigarette Dependence (FTCD)

Please answer each question below by checking (x) your answer in the box (□).

1. How soon after you wake up do you smoke your first cigarette?
 Within 5 minutes
 6 - 30 minutes
 31 - 60 minutes
 After 60 minutes
2. Do you find it difficult to refrain from smoking in places where it is forbidden (e.g., in church, at the library, in the cinema, etc.)?
 Yes
 No
3. Which cigarette would you hate most to give up?
 The first one in the morning
 Any other
4. How many cigarettes per day do you smoke?
 31 or more
 21 - 30
 11 - 20
 10 or less
5. Do you smoke more frequently during the first hours after waking than during the rest of the day?
 Yes
 No
6. Do you smoke if you are so ill that you are in bed most of the day?
 Yes
 No

APPENDIX 2: Brief Questionnaire of Smoking Urges (QSU-Brief)

For each item, please indicate how you feel RIGHT NOW.

1. I have a desire to smoke right now.

Strongly
Strongly
Disagree
Agree

2. Nothing would be better than smoking right now.

Strongly
Strongly
Disagree
Agree

3. If it were possible, I probably would smoke right now.

Strongly
Strongly
Disagree
Agree

4. I could control things better right now if I could smoke.

Strongly
Strongly
Disagree
Agree

5. All I want right now is a cigarette.

Strongly
Strongly
Disagree
Agree

6. I have an urge for a cigarette.

Strongly
Strongly
Disagree
Agree

7. A cigarette would taste good now.

Strongly
Strongly
Disagree
Agree

8. I would do almost anything for a cigarette now.

Strongly
Strongly
Disagree
Agree

9. Smoking would make me less depressed.

Strongly
Strongly
Disagree
Agree

10. I am going to smoke as soon as possible.

Strongly
Strongly
Disagree
Agree

APPENDIX 3: Minnesota Nicotine Withdrawal Scale - Revised (MNWS-R)

Please rate yourself for the last day

Scale: 0 = none, 1 = slight, 2 = mild, 3 = moderate, 4 = severe

1. Angry, irritable, frustrated	0	1	2	3	4
2. Anxious, nervous	0	1	2	3	4
3. Depressed mood, sad	0	1	2	3	4
4. Desire or craving to smoke	0	1	2	3	4
5. Difficulty concentrating	0	1	2	3	4
6. Increased appetite, hungry, weight gain	0	1	2	3	4
7. Insomnia, sleep problems, awakening at night	0	1	2	3	4
8. Restless	0	1	2	3	4
9. Impatient	0	1	2	3	4
10. Constipation	0	1	2	3	4
11. Dizziness	0	1	2	3	4
12. Coughing	0	1	2	3	4
13. Dreaming or nightmares	0	1	2	3	4
14. Nausea	0	1	2	3	4
15. Sore throat	0	1	2	3	4

APPENDIX 4: Perceived Health Risk Scale

On the scale below, indicate your perception of the risk of becoming addicted to the cigarette you are currently using.

Very
low
risk

Very
high
risk

1. INTRODUCTION

The following statistical analysis plan (SAP) provides the framework for the summarization of the data from this study. The SAP may change due to unforeseen circumstances. Any changes made from the planned analysis within protocol, after locking of the database will be documented in the clinical study report (CSR).

Any additional analyses not addressed within this SAP and/or driven by the data, or requested by the SPONSOR, will be considered out of scope and must be described in the CSR.

2. STUDY PURPOSE, HYPOTHESIS, OBJECTIVES AND ENDPOINTS

2.1 Study Purpose

The purpose of this study is to examine whether measures of cigarette consumption behavior (cigarettes per day and smoking topography) are changed when smokers switch from smoking conventional cigarettes to smoking cigarettes with a very low nicotine (VLN) content (0.4 mg nicotine per gram of tobacco). Secondary purposes are to examine changes in biomarkers of exposure (BoE), nicotine pharmacokinetics (PK) and subjective measures of dependence, smoking urges, withdrawal symptoms and perceived health risks, when subjects switch to smoking VLN cigarettes.

2.2 Hypothesis

It is anticipated that when adult smokers switch to smoking VLN cigarettes, after habitually consuming their usual quantity and brand of cigarettes, their daily cigarette consumption will be reduced. It is further anticipated that puffing topography parameters will be unchanged following smoking VLN cigarettes for 6 weeks (i.e. no smoking compensation will occur).

2.3 Objectives

Primary objectives:

1. To characterize cigarette consumption behavior (cigarettes per day and puffing topography) before, during and after a switch from usual brand (UB) to VLN cigarettes for 6 weeks.

Secondary objectives:

1. To evaluate changes in tobacco-related biomarkers of exposure (BoE) before, during and after a 6-week switch from UB to VLN cigarettes.
2. To evaluate nicotine PK before, during and after a 6-week switch from UB to VLN cigarettes.
3. To evaluate changes in subjective effects before, during and after a 6-week switch from UB cigarettes to VLN cigarettes.

2.4 Endpoints

Product Use Endpoints (Primary Objective 1):

- Cigarettes smoked per day (CPD). Both compliant and non-compliant smoking captured in the electronic diaries (e-diaries).
- Number of collected used cigarette butts (apparent compliant, apparent non-compliant, and total)
- Puffing topography parameters (puff duration, puff volume, peak puff flow rate, average flow rate and inter-puff interval)

BoE Endpoints (Secondary Objective 1):

- In urine:
 - Total 4-(methylnitrosamino)-1-(3-pyridyl)-1-butanol (NNAL; 4-(methylnitrosamino)-1-(3-pyridyl)-1-butanone [NNK] biomarker)
 - Total N-Nitrosomoninicotine (NNN)
 - 3-hydroxypropylmercapturic acid (3-HPMA; acrolein biomarker),
 - S-phenylmercapturic acid (S-PMA; benzene biomarker),
 - 1-hydroxypyrene (1-OHP; hydroxypyrene biomarker)
 - Total nicotine equivalents (Tneq)
 - Creatinine concentration (for normalization of urinary BoE endpoints)
- Carboxyhemoglobin in blood
- Cotinine in plasma

Nicotine PK Endpoints(Secondary Objective 2)

- Nicotine PK parameters will include Cmax, AUC0-180 and Tmax

Subjective Effects Endpoints (Secondary Objective 3)

- Fagerström Test for Cigarette Dependence (FTCD)
- Brief Questionnaire of Smoking Urges (QSU-Brief)
- Minnesota Nicotine Withdrawal Scale - Revised (MNWS-R)
- Perceived health risk scale
- Safety endpoints will include adverse events (AEs).

3. STUDY DESIGN

This is an open-label, randomized, forced-switching study to be conducted at multiple study sites. Seventy (70) self-affirmed exclusive filtered non-mentholated cigarette smokers and 70 self-affirmed exclusive filtered mentholated cigarette smokers will be enrolled and begin the study at Week -1.

All potential subjects will provide informed consent and successfully complete the Screening procedures prior to participation in the study. Subjects will also engage in a

brief product trial with the VLN cigarettes. Subjects who react negatively (i.e., unwilling to use and/or cannot tolerate the product [experience AEs that will prevent them from continuing to use the product as judged by the Investigator]) to the VLN cigarettes during the product trial period will not continue in the study.

At the start of Week -1, all subjects will be asked to smoke their UB cigarettes as per their usual daily consumption for the following week. Subjects will receive an e-diary to record daily cigarette use (CPD). Training in completion of the e-diary will be provided at the visit at the start of Week -1.

Subjects will return at the end of Week -1, at the time indicated by the clinical research unit (CRU), for collection of blood and 24-hour urine samples for baseline BoE assessments. Subjective questionnaires for dependence, withdrawal symptoms, urges to smoke, and perceived health risk will also be completed at scheduled times. A randomly-selected subset of 18 non-menthol and 18 menthol smoker subjects will complete an assessment of puffing topography with their UB cigarettes during this visit. A further subset of 12 of the non-menthol and 12 of the menthol smoker subjects who complete the topography assessment will also complete a nicotine PK assessment at the end of this visit. Subjects who undergo topography and PK assessments will be assigned to switch to smoking VLN cigarettes.

On Day -1 of Week 1, subjects will be randomly selected to either remain smoking their non-menthol (20 subjects) or menthol (20 subjects) UB cigarettes, or to switch to smoking non-menthol (50 subjects) or menthol (50 subjects) VLN cigarettes as per their UB cigarette flavor. Subjects will return at the end of Weeks 2 and 6, at the time indicated by the CRU, for collection of blood and 24-hour urine samples for BoE assessments. Subjective effects questionnaires will also be completed at scheduled times. Subjects will continue recording their CPD in their e-diaries. The same subset of 18 non-menthol and 18 menthol smoker subjects selected to complete a puffing topography assessment with their UB cigarette on Week-1, will complete an assessment of puffing topography with the VLN cigarettes at these visits, and a further subset of 12 non-menthol and 12 menthol smoker subjects will also complete an assessment of nicotine PK at the end of these visits. Subjects undergoing topography and PK assessments will have been assigned to switch to smoking VLN cigarettes.

Additionally, all subjects will visit the clinic at the end of Week 4 to receive further supplies of cigarettes (if assigned to the VLN groups) and to complete subjective effects questionnaires.

Subjects randomized to the VLN groups will be provided with a supply of VLN cigarettes at each visit, which will be 150 % of their usual daily consumption as reported during Week 1. If a subject runs out of cigarettes between clinic visits, they may visit the clinic to receive additional test cigarettes. All subjects will be asked to smoke their cigarettes *ad libitum*, recording their actual daily consumption in their e-diaries. Non-compliant nicotine product consumption should also be recorded. Used

cigarette butts will also be collected during ambulatory periods to verify product use and/or assess compliance. During Week 1 (all subjects) and all subsequent weeks (subjects randomized to continue smoking UB cigarettes) subjects will be asked not to change their UB cigarette brand or flavor.

The CRU will attempt to contact all subjects who participated in the study (including subjects who terminate the study early) using their standard procedures approximately 7 days after the last contact to determine if any AE has occurred since the last study visit.

4. SAMPLE SIZE ESTIMATION

4.1 Cigarette Consumption

An intended sample size of 50 subjects in each of the two groups who switch from smoking usual brand to VLN cigarettes has been set for this study. This is based on powering the primary objective of a within-group comparison of cigarette consumption at baseline and end-of-study. The calculation was based on the number of pairs required to perform a one-tailed paired t-test with 80% power and an alpha level of 0.05 for a decrease in cigarette consumption of 3 CPD compared to available historical consumption data. The sample size was determined to be adequate based on potential non-compliance with the use of VLN cigarettes. A lower number (20) of smokers will be randomized to the continue-to-smoke usual brand groups, given the lower variability in consumption data and lower non-compliance anticipated in these groups. This will provide sufficient power for the secondary objective of between-group comparisons in cigarette consumption.

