6.1 Sample Size Estimation

6.1.1 Cigarette consumption

An intended sample size of 50 subjects in each of the two groups who switch from smoking usual brand to VLN cigarettes has been set for this study. This is based on powering the primary objective of a within-group comparison of cigarette consumption at baseline and end-of-study. The calculation was based on the number of pairs required to perform a two-tailed paired t-test with 80% power and an alpha level of 0.05 for a decrease in cigarette consumption of 3 CPD compared to available historical consumption data (2, 4). The sample size was determined to be adequate based on potential non-compliance with the use of VLN cigarettes (2). A lower number (20) of smokers will be randomized to the continue-to-smoke usual brand groups, given the lower variability in consumption data and lower non-compliance anticipated in these groups. This will provide sufficient power for the secondary objective of between-group comparisons in cigarette consumption.

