4.2 Puffing Topography

An intended sample size of 12 subjects in each of the two groups who switch from smoking usual brand to VLN cigarettes has been set for this study. This is based on powering the primary objective of a within-group comparison of puffing topography parameters at baseline and end-of-study. The calculation was based on the number of pairs required to perform a two-tailed paired t-test with 80% power and an alpha level of 0.05 to detect significant differences between UB and VLN cigarettes and is based on available puffing topography data (5). This sample size will also provide sufficient power to detect differences in nicotine PK between UB and VLN cigarettes.

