7.3 Statistical Analysis of Primary Endpoints

Paired t-tests will be used to compare cigarette consumption (CPD) and puffing topography parameters at the Week 2 and Week 6 time points with the baseline (Week -1) values. This analysis will be conducted on the evaluable subjects in the PP population. If data are unexpectedly found not to be normally distributed, an appropriate non-parametric test will be performed. Differences will be considered statistically significant at an alpha level of 0.05. Means, difference of means, 90% confidence interval for difference, and p-value will be presented.

The following SAS codes will be used for the analysis:

```
Proc ttest data=<>;  
By product_group;  
Paired week_X*baseline;  
Run;
```

Where week_X will be either Week 2 or Week 6. Product Groups are VLN non-mentholated, VLN non-mentholated, and VLN combined which pooled non-mentholated and mentholated groups. The primary analysis will be based on the VLN combined product group.

In addition, a linear mixed model analysis of variance will be used to compare the between product group differences in the absolute change from baseline values of the consumption and puffing topography parameters. Product group, week, and product group by week interaction will be the fixed factors in the model. A restricted maximum likelihood estimation method with an unstructured (UN) covariance structure will be applied. If the model does not converge, the first order autoregressive AR(1) and/or compound symmetry CS covariance structures will be tested as alternatives. The least-square mean difference, 95% confidence interval and p-value will be provided for the product group difference. The pairwise comparisons (VLN non-mentholated versus UB non-mentholated, VLN mentholated versus UB mentholated, and VLN combined versus UB combined) will be performed at week Week 2 and Week 6. Least-square means (LSMeans), difference of LSMeans, 90% confidence interval for difference, and p-value for difference will be presented.

The following SAS codes will be used to perform the analysis.

```
Proc mixed data=<>;  
Class subject product_group week;  
Model response = product_group week product_group*week /ddf=kr;  
Repeated week/type=<type> subject=subject;  
LSmeans product_group*week/CL alpha=0.05 CL pdiff;  
Run;
```

The primary analysis will be the pairwise comparisons of VLN combined versus UB combined (pooled non-mentholated and mentholated groups).

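### The cigarettes-per-day sample size is two-tailed in the protocol and one-tailed in the SAP, and SAP 7.3 gives conflicting confidence levels for the primary endpoints

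*SAP*

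**What the plan says.** **Sample size.** Protocol 6.1.1 sizes the cigarettes-per-day (CPD) comparison with a "two-tailed paired t-test with 80% power and an alpha level of 0.05 for a decrease in cigarette consumption of 3 CPD". SAP 4.1 has an almost identical paragraph, with the same 50 per VLN group, but specifies a "one-tailed paired t-test with 80% power and an alpha level of 0.05 for a decrease in cigarette consumption of 3 CPD". Neither gives the SD of the within-subject differences. Both mention non-compliance without a rate; the SAP's wording is "The sample size was determined to be adequate based on potential non-compliance with the use of VLN cigarettes". SAP 4.2 keeps topography as a "two-tailed paired t-test with 80% power and an alpha level of 0.05 to detect significant differences between UB and VLN cigarettes". SAP 12 declares the SAP's analyses aligned with the protocol and lists no changes.

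**Analysis.** SAP 7.3 sets significance at alpha 0.05 without saying one- or two-sided. The interval levels are:

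- Paired t-test, text: "Means, difference of means, 90% confidence interval for difference, and p-value will be presented".
- Paired t-test, code: the statement is "Paired week_X*baseline", with no level or sidedness option anywhere in the step.
- Mixed model, text: a 95% interval for the product-group difference, then a 90% interval for the difference of least-squares means.
- Mixed model, code: the LSMEANS line carries `alpha=0.05`.

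SAP 9.5 asks for a 90% interval for the geometric mean ratio and reuses the paired-test code. SAP 8.4 and 10.3 also reuse the 7.3 code. The table shells leave the level as `XX%`.

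SAP 7.3 also states: "The primary analysis will be based on the VLN combined product group".

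**The concern.** The 80% power claim refers to a different test in each document, so a reader cannot tell which one was calculated. Because SAP 7.3 never states sidedness, the sample-size paragraph in SAP 4.1 is the only place where the SAP says anything about it for CPD, and there it contradicts the protocol.

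The interval level raises the same doubt. A 90% interval is the natural companion of a one-sided 0.05 test, and the hypothesis in SAP 2.2 is directional: "their daily cigarette consumption will be reduced". Together these could be read as an unrecorded move to one-sided testing of a primary endpoint. The same section also says 95%, so a programmer cannot satisfy all of it. At stake are the stated per-group power and the error bars on the primary endpoints.

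**Working it through.** **Inputs.** Decrease of 3 CPD, alpha 0.05, 80% power and n = 50 per VLN group (Protocol 6.1.1, SAP 4.1); up to 100 pairs for VLN combined (2 × 50). The SD of the differences is not given, so every SD below is an assumption.

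**Method.** Exact power of a paired t-test: T is noncentral t with n − 1 df and noncentrality (3/SD)·√n. The critical value is t(0.95) one-tailed or t(0.975) two-tailed.

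**Can 50 be reproduced?** Not without the SD. Solving instead for the SD at which n = 50 gives exactly 80%:

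- Two-tailed: 3/SD = 0.4042, so SD = 7.42.
- One-tailed: 3/SD = 0.3566, so SD = 8.41.

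If 50 is the bare requirement, the two documents imply different SDs. If 50 includes a non-compliance allowance, one SD can satisfy both:

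| Assumed SD | Pairs for 80%, two-tailed | Pairs for 80%, one-tailed | Two-sided power, n = 50 | Two-sided power, n = 100 |
|---|---|---|---|---|
| 6.5 | 39 | 31 | 89% | >99% |
| 7 | 45 | 36 | 84% | 99% |
| 7.42 | 50 | 40 | 80% | 98% |
| 8 | 58 | 46 | 74% | 96% |
| 8.41 | 64 | 50 | 70% | 94% |

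Suppose the sizing was one-tailed and the allowance is fully used up, leaving 31, 36 or 46 evaluable pairs at SD 6.5, 7 or 8. Two-sided power is then 70% to 71% per flavour group, and about 95% for VLN combined (62, 72 or 92 pairs).

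**Interval against p-value.** A 90% interval excludes zero exactly when the two-sided p-value is below 0.10. Beside a two-sided 0.05 test the two disagree when 0.05 < p < 0.10. The probability of that is power at alpha 0.10 minus power at alpha 0.05:

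- No true effect: 0.10 − 0.05 = 5%.
- True 3 CPD decrease, n = 50: 5.0%, 6.7%, 8.0%, 9.5% and 10.4% at SD 6.5, 7, 7.42, 8 and 8.41.
- True 3 CPD decrease, n = 100: 0.3%, 0.7%, 1.2%, 2.1% and 2.9% at the same SDs.

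These use full enrolment. The analysis is on the per-protocol population, so evaluable pairs may be fewer.

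**Width.** The ratio of 95% to 90% width is t(0.975)/t(0.95):

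- 49 df: 2.010/1.677 = 1.20.
- 99 df: 1.984/1.660 = 1.20.
- PK subset: 1.21 at 23 df (24 subjects) and 1.23 at 11 df (12 subjects).

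**Which sidedness do the documents favour?** For one-sided: SAP 4.1, the directional hypothesis and the 90% intervals. For two-sided: Protocol 6.1.1, the 95% sentence and `alpha=0.05` in the mixed-model code. No analysis section states a one-sided test, and topography gets the same 90% interval although SAP 4.2 sizes it two-tailed. The balance is towards two-sided, but the SAP does not say so.

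**The case against.** The strongest reply is that these are two separate wording slips with no demonstrated effect on a conclusion. Sidedness appears only in the sample-size rationale; n and the analysis rule (paired t-tests at alpha 0.05, in Protocol 6.3.7 and SAP 7.3) are unchanged. A 90% interval beside a 0.05 test is not in itself an error, since nothing makes the interval a decision rule. For the paired test the text names only one level. The two mixed-model sentences might describe two outputs, `XX%` is an ordinary placeholder, and what the paired-test code would print depends on software defaults that the documents do not state.

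Much of this stands. No shortfall is shown, the power figures are all conditional, and a placeholder is harmless where the text fixes the level. The two-outputs reading does not stand. The shells for the between-group comparisons (Tables 14.2.1.1.3 and 14.2.3.3) have a single interval column for the same pairwise comparisons at Weeks 2 and 6, and the printed LSMEANS line covers only product group by week. For those tables the text does not fix the level, so the placeholder leaves it open. For the paired test, text and code still need to be made to agree.

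**Conclusion.** The inconsistency is established from the text: two-tailed against one-tailed for the same n, effect, power and alpha, with no change recorded, and 95% against 90% for the same mixed-model difference. Neither an arithmetic error nor a switch to one-sided testing is proven.

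Only the stated per-flavour-group power is in doubt, and only if the sizing really was one-tailed. In that case two-sided power is about 70% at the one-tailed requirement, whatever the SD in the range examined. VLN combined stays at 94% or more in the cases examined, all of which assume a true decrease of 3 CPD and an SD of 8.41 or less.

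The reporting problem takes one of two forms. If the 90% text is followed, intervals and two-sided p-values will sometimes disagree. If the paired-test code is run as printed, and the software defaults to two-sided 95% output (an assumption), the two agree but a 95% interval would be labelled 90%. This should be fixed; it does not threaten the primary analysis.

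**What to change.** 1. Retrieve the original calculation and make Protocol 6.1.1 and SAP 4.1 agree, stating the SD and the non-compliance allowance used. If it was two-tailed, correct SAP 4.1. If it was one-tailed, restate the two-sided per-group power and record the change in SAP 12.
2. State two-sided alpha 0.05 in SAP 7.3. Use 95% intervals in the text, set the level explicitly in the paired-test code, and replace `XX%` in the shells serving SAP 7.3, 8.4 and 10.3.
3. In SAP 9.5, either move the ratio interval to 95%, or keep 90% with a stated reason and an explicit level in the code.
4. If one-sided testing of CPD was intended, say so in SAP 7.3 and SAP 12. Protocol section 6 requires an amendment for a major change to a primary analysis.

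The cost is wording, one code option, shell headers and looking up the calculation. Reported intervals will be about 20% wider than the 90% ones, and the stated per-group power may turn out less favourable.
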